16.4.1. Clinically Noteworthy ECG Criteria

Clinically noteworthy quantitative ECG measurements will be identified in accordance with the following criteria:

- Absolute values for QTcF will be classified as:
 - 450 msec and <=480 msec
 - > 480 msec and <=500 msec
 - > 500 msec
- Change from Baseline for QTcF will be classified as:
 - Increase from baseline >30 msec and <=60 msec
 - Increase from baseline >60 msec

16.5. Vital Signs

The following Vital Signs measurements will be reported for this study: systolic and diastolic blood pressure, pulse rate, respiratory rate, heart rate, oxygen saturation, and body temperature.

The following summaries will be provided for vital signs data:

- Actual and change from baseline by visit and treatment

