- e. Scheduled safety ECG by site for in-time evaluation of ECGs. Timepoints will be from the start of the triplicate assessment as indicated. Single ECG will be collected at the 10 and 30 minutes post EOI timepoints.
- f. Vital signs can be taken any time prior to randomization on Admission/Day -1.
- g. On Day 1, ASQ will be completed predose (within 60 minutes prior to dosing) and approximately 10 minutes (+15 minutes), 1 hour (+15 minutes), and 2 hours (+15 minutes) postdose. This assessment will be performed after completion of all other simultaneously scheduled procedures to avoid interference with scheduled vital sign, ECG, and PK evaluation (see [Section 8.2.4](#)).
- h. On Day 1, the injection site will be evaluated prior to study treatment administration and again immediately after study treatment administration, in approximately hourly (+15 minutes) intervals for up to 6 hours postdose. Injection site assessment also occurs any time on Day 2, and any time prior to discharge from the CRU on Day 3 (see [Section 8.2.1.1](#) for details on the 4 point scale injection site assessment).
- i. If the duration of the short 10 minute infusion exceeds 15 minutes, or an interruption occurs that exceeds the duration of infusion to more than 15 minutes, for PK blood collection (postdose) up and including 3 hours, every effort should be made to follow the time relative to the end of infusion.
- j. Blood pressure measurements for 5 minutes post start of infusion, at EOI, and 20 minute post EOI timepoints will be single readings.

The timing of PK (both plasma and urine), safety ECG, and vital sign assessments may be adjusted based on emerging data. Furthermore, in case that CS-1103 half-life is less than 4 hours, Holter recording may be discontinued at a time earlier than 24 hours post IV infusion. Furthermore, up to 2 additional blood collections may be added on Day 1, Day 2, or Day 3; pooled urine collections may be extended, and discharge may be delayed for up to 8 hours to optimize PK assessment without preparation of an amendment.

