9.3.3 Safety Analyses

All safety analyses will be performed on the Safety Analysis Population. Adverse events will be coded using the latest version of the Medical Dictionary for Regulatory Activities (MedDRA). The overall number and percentage of participants with at least one AE (and SAE) will be tabulated. Placebo participants will be combined into 1 treatment cohort. Overall, AE data will be summarized by treatment received. The frequency of all treatment emergent AEs (TEAEs), TEAEs by severity as detailed in [Section 10.3](#). All TEAEs by relationship to study treatment, SAEs, TEAEs leading to death, and TEAEs leading to discontinuation of the study will be tabulated by Preferred Term (PT) and System Organ Class (SOC) for each treatment cohort. Summary statistics, including change from baseline, for vital signs, laboratory parameters, and ECG intervals will be provided by treatment, visit, and time point, as appropriate. Shift tables for laboratory parameters at each postbaseline visit will be tabulated against baseline results showing frequency of laboratory parameter observed normal range indicator (Low, Normal, High). For ECG results, appropriate outlier tabulations for QT and QTcF will also be presented by treatment. Outliers for QT and QTcF defined under outcome measures will be summarized using counts and percentages by treatment and sampling time, if appropriate and using participant-level maximum over time by treatment. The following categories will be presented by treatment and overall for CS-1103:

- Outlier QT and QTcF intervals (450-480 ms, 480-500 ms and >500 ms)
- Change from baseline in QT and QTcF intervals (30-60 ms and >60 ms)

Results of the physical examinations (including injection site assessment) and the AQS will be listed and if appropriate, summarized by treatment.

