2. STUDY OBJECTIVES

Objectives	Endpoints
Primary	

• To assess the safety and tolerability of CS-1103, administered by IV infusion	
Standard safety and tolerability parameters but not limited to:
 
• Adverse Events• Vital signs (blood pressure, pulse rate, respiratory rate, oxygen saturation, and body temperature)• Digital 12-lead ECGs/Holter• Laboratory parameters (clinical chemistry, hematology, coagulation, urinalysis)
Secondary	

• To characterize the PK of CS-1103, administered by IV infusion	
Plasma and urine PK parameters including but not limited to:
 
• C_{max}, t_{max}, C_{EOI}, $AUC_{(0-last)}$, $AUC_{(0-inf)}$, $t_{1/2}$, λ_z, CL, V_{ss}, and V_z• By-interval and cumulative CS-1103 excretion in urine (A_e and f_e)• CL_r

Objectives	Endpoints
Exploratory	

To explore the relationship between CS-1103 plasma concentrations and changes in QT intervals during dosing, if anyAbbreviations: AE = adverse event; A_e = amount; AUC = area under the concentration versus time curve; AUC_(0-inf) = AUC from time zero extrapolated to infinity; AUC_(0-last) = AUC from time zero to the last quantifiable concentration; C_{EOI} = concentration at the end of 10-minute IV infusion; CL = systematic clearance; CL_r = renal clearance; C_{max} = maximum concentration; ECG = electrocardiogram; f_e = fraction; IV = intravenous; λ_z = elimination rate constant; PK = pharmacokinetics; t_{1/2} = half-life; QTcF = QT corrected for heart rate by Fridericia's formula; t_{max} = time to C_{max}; V_{ss} = volume of distribution at steady-state following intravenous dosing; V_z = volume of distribution following intravenous dosing.	
Concentration-QT correlation performed on baseline-corrected QTcF time-matched with PK. Concentration-QT correlation may be reported separately from the clinical study report

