3.3. Changes to Analysis from Protocol

Serious adverse events (SAEs), TEAEs leading to death and TEAEs leading to discontinuation from study will be listed.

[REDACTED]

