8. OUTPUT PRESENTATIONS

Appendix 1 shows conventions for presentation of data in outputs.

The output shells provided with this SAP describe the presentations for this study and therefore the format and content of the summary tables, figures, and listings to be provided by IQVIA Biostatistics.

Some minor modifications may be necessary to the planned design of tables, figures, and listings to accommodate data collected during the actual study conduct.

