16.4. ECG Evaluations

The following ECG data will be reported for this study: PR, QRS, QT, QTcF, and HR. Replicate measurements will be averaged for use in summary tables.

Assessment of ECG (Investigator’s judgment) for each parameter will be recorded as following:

- Normal
- Abnormal, Not Clinically Significant (NCS)
- Abnormal, Clinically Significant (CS)

The following summaries will be provided for ECG data:

- Actual and change from baseline by visit, timepoint and treatment
- Number (%) of subjects with clinically noteworthy values postdose
- Listing of subjects with clinically noteworthy values

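### SAP 16.5 leaves out the time point that the protocol specifies for vital-sign summaries, so a transient change around the infusion could be diluted in the only planned table

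*SAP*

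**What the plan says.** SAP 16.5 lists the vital signs to be reported and plans one summary for them: "Actual and change from baseline by visit and treatment". It defines no outlier or threshold category.

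Protocol 9.3.3 states that summary statistics for "vital signs, laboratory parameters, and ECG intervals will be provided by treatment, visit, and time point, as appropriate". The protocol synopsis says the same.

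For ECGs, SAP 16.4 plans "Actual and change from baseline by visit, timepoint and treatment", together with counts and a listing of clinically noteworthy values.

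SAP 3.3, on changes from the protocol, contains one legible statement: "Serious adverse events (SAEs), TEAEs leading to death and TEAEs leading to discontinuation from study will be listed". A further line is redacted.

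Vital signs are among the endpoints for the primary objective in SAP 2: "Vital signs (blood pressure, pulse rate, respiratory rate, oxygen saturation, and body temperature").

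In the protocol's Schedule of Activities (section 1.3), Day 1 is a single visit column, and the detailed schedule sets several vital-sign times within it. Its footnote j reads: "Blood pressure measurements for 5 minutes post start of infusion, at EOI, and 20 minute post EOI timepoints will be single readings".

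**The concern.** This is a first-in-human study of a 10-minute infusion, and protocol 4.2 expects a short half-life. A drug effect on blood pressure, pulse, respiration or oxygen saturation would most plausibly appear during the infusion or soon after it. The useful group summary is therefore the change from baseline at each scheduled time, by dose, against pooled placebo. The protocol planned that summary. The SAP text does not.

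Two features of the SAP make the omission matter more. It distinguishes the two wordings: ECGs are summarised with the time point, while laboratory results are summarised by visit and treatment. Vital signs are serial like the ECGs but carry the laboratory wording, so a programmer could take the difference as intended. There is also no second table to fall back on, because SAP 16.5 has nothing like the noteworthy-value counts planned for ECGs.

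**Working it through.** The documents give no figure to reproduce; this is a comparison of wording, followed by one conditional illustration.

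**1. The texts side by side**

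| Place | Data | Summary level |
|---|---|---|
| Protocol 9.3.3 and synopsis | Vital signs, laboratory, ECG | Treatment, visit and time point, where appropriate |
| SAP 16.4 | ECG | Visit, time point, treatment |
| SAP 16.3 | Laboratory | Visit, treatment |
| SAP 16.5 | Vital signs | Visit, treatment |

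SAP 16.5 drops a level that the protocol names.

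**2. How many readings the Day 1 visit holds**

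Footnote j gives three times after the start of infusion: 5 minutes in, end of infusion (EOI), and 20 minutes after EOI. The extracted schedule table is broken, but readings at 3, 6 and 8 hours are legible. That makes at least 3 + 3 = 6, plus the predose reading. The true count may be higher.

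**3. Whether another SAP rule fills the gap**

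- SAP 6.6 chooses among retests of the same scheduled time. It does not say how different scheduled times enter a visit-level summary.
- SAP 6.7 defines change from baseline per visit and does not mention time points.
- SAP 6.5 settles the baseline (a planned predose reading on the dosing day counts as pre-baseline) but not the postdose rows.
- Appendix 1 takes visit labels from the eCRF, which is not among the documents.
- SAP 8 says "The output shells provided with this SAP describe the presentations for this study". The shells are not among the documents either.

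No rule says that Day 1 readings are averaged, and none says that they are kept apart.

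**4. Illustration, if they were averaged**

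Assume a change of size D is present at m of k postdose readings, is absent at the others, and the k readings are averaged with equal weight. The visit value then shifts by D × m / k. D and m are assumed. For k, 6 is the legible minimum and 12 an assumed upper value.

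| D (mmHg) | m | k = 6 | k = 12 |
|---|---|---|---|
| 20 | 2 | 20 × 2/6 = 6.7 | 20 × 2/12 = 3.3 |
| 20 | 1 | 20 × 1/6 = 3.3 | 20 × 1/12 = 1.7 |

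One or two affected readings would thus appear at 8% to 33% of their size. With rows by time point, the full change appears at the time it occurs.

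**The case against.** A reader might infer that the SAP puts all Day 1 readings into one row and so hides an effect at the peak. The documents do not support that.

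- No section states an averaging or pooling rule; a missing rule is not a collapsing rule. The layout is left to shells that may already show time points.
- SAP 6.6 is written in terms of the scheduled time, which fits poorly with a single averaged Day 1 value. SAP 16.5 repeats the laboratory bullet of SAP 16.3, so a carried-over line is at least as plausible as a decision to collapse serial data.
- Individual changes stay visible. SAP 6.6 puts all scheduled and unscheduled data in listings, and protocol 10.3.1 makes abnormal vital signs judged clinically significant adverse events. With 6 active participants per cohort, profiles can be read directly.
- The study tests no hypotheses. None of the quantitative dose-escalation stopping criteria in protocol 4.6.1 uses a vital-sign summary table, and the Safety Review Committee's data review is governed by its charter.
- The protocol wording is qualified by appropriateness, and the redacted line in SAP 3.3 could declare the change.

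Most of this stands, and it limits the consequence to possible dilution in a summary table. It does not remove the conflict. Serial readings around a short infusion are a clear case where a time-point summary is appropriate, as the SAP accepts for ECGs. Listings do not give group means by dose against placebo. If the shells do show time points, SAP 16.5 disagrees with its own shells and needs the same correction.

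**Conclusion.** SAP 16.5 is wrong as written: it conflicts with protocol 9.3.3 on the summary level for a primary safety endpoint, and no legible text declares or justifies the departure. That much rests on the wording alone.

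The consequence is conditional. It arises only if the tables are programmed literally by visit, and its size depends on how readings would then be combined. The mmHg figures in the illustration rest on an assumed change, an assumed number of affected readings, equal-weight averaging and 6 to 12 readings. They are not estimates for this drug. Nothing in the documents shows that the wording would change a dose-escalation decision. The point is worth correcting before the final analysis but does not threaten the study.

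**What to change.** Replace the bullet in SAP 16.5 with the wording already used in SAP 16.4, "Actual and change from baseline by visit, timepoint and treatment", and check that the vital-sign output shells have a row for each scheduled Day 1 time. Keep the baseline definition in SAP 6.5: it already treats a planned predose reading as pre-baseline and allows an earlier value when that reading is missing, so no separate Day 1 reference rule is needed. If a visit-level summary is intended, state it as a change in SAP 3.3 with the reason and the rule for combining readings.

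The cost is one SAP line, a shell check and a longer table. The readings are already scheduled by time point, so no new data collection is needed.

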16.6. Physical Examination

Physical examination results will be listed. Clinically significant findings will be recorded under Medical/Surgical History up to screening and under Adverse Events post screening.

16.7. Injection Site Assessment

[figure not shown]
Result of injection site assessment will be listed.

16.8. Anxiety Symptoms Questionnaire

Anxiety Symptoms Questionnaire (ASQ) results will be listed.

[figure not shown]
17. DATA NOT SUMMARIZED OR PRESENTED

Comments will not be summarized or presented but will be available in clinical study database.

18. REFERENCES

There are no references.

APPENDIX 1. PROGRAMMING CONVENTIONS FOR OUTPUTS

IQVIA Output Conventions

Outputs will be presented according to the IQVIA Global Biostatistics Standard Output Conventions, which is available upon request.

Dates & Times

Depending on data availability, if not otherwise specified, dates will take the format DDMMMYYYY; times will take the format hh:mm; combined dates and time will take the format DDMMMYYYY/hh:mm.

Spelling Format

English US.

Presentation of Treatment Groups

For outputs, treatment groups will be represented as follows, as appropriate:
Placebo, CS-1103 xx mg/kg, All Active (when applicable), All Subjects.

[figure not shown]
Presentation of Visits

For outputs, visits will be represented as collected on eCRF, as appropriate.

Listings

All listings will be ordered by the following (unless otherwise indicated in the template):

- Cohort/Treatment (cohort only presented when applicable)
- Subject number
- Date and Time (where applicable) of assessment
- For listings where non-randomized subjects are included (if applicable), these will appear in a category after the randomized treatment groups labeled 'Not Randomized'

APPENDIX 2. PARTIAL DATE CONVENTIONS

Imputed dates will NOT be presented in the listings.

Algorithm for Treatment Emergence of Adverse Events:

START DATE	STOP DATE	ACTION
Known	Known/Partial/ Missing	If start date < study med start date, then not TEAE If start date >= study med start date, then TEAE
Partial, but known components show that it cannot be on or after study med start date	Known/Partial/ Missing	Not TEAE
Partial, could be on or after study med start date OR Missing	Known	If stop date < study med start date, then not TEAE If stop date >= study med start date, then TEAE
	Partial	Impute stop date as latest possible date (i.e. last day of month if day unknown or 31st December if day and month are unknown), then: If stop date < study med start date, then not TEAE If stop date >= study med start date, then TEAE
	Missing	Assumed TEAE

Algorithm for Prior / Concomitant Medications:

START DATE	STOP DATE	ACTION
Known	Known	If stop date < study med start date, assign as prior If stop date >= study med start date and start date <= study med end date, assign as concomitant If stop date >= study med start date and start date > study med end date, assign as post study
	Partial	Impute stop date as latest possible date (i.e. last day of month if day unknown or 31st December if day and month are unknown), then: If stop date < study med start date, assign as prior If stop date >= study med start date and start date <= study med end date, assign as concomitant If stop date >= study med start date and start date > study med end date, assign as post treatment
	Missing	If stop date is missing could never be assumed a prior medication If start date <= study med end date, assign as concomitant If start date > study med end date, assign as post treatment
Partial	Known	Impute start date as earliest possible date (i.e. first day of month if day unknown or 1st January if day and month are unknown), then: If stop date < study med start date, assign as prior If stop date >= study med start date and start date <= study med end date, assign as concomitant If stop date >= study med start date and start date > study med end date, assign as post treatment

START DATE	STOP DATE	ACTION
	Partial	
Impute start date as earliest possible date (i.e. first day of month if day unknown or 1st January if day and month are unknown) and impute stop date as latest possible date (i.e. last day of month if day unknown or 31st December if day and month are unknown), then:
 
If stop date < study med start date, assign as prior
 
If stop date \geq study med start date and start date \leq study med end date, assign as concomitant
 
If stop date \geq study med start date and start date $>$ study med end date, assign as post treatment

	Missing	
Impute start date as earliest possible date (i.e. first day of month if day unknown or 1st January if day and month are unknown), then:
 
If stop date is missing could never be assumed a prior medication
 
If start date \leq study med end date, assign as concomitant
 
If start date $>$ study med end date, assign as post treatment

Missing	Known	
If stop date < study med start date, assign as prior
 
If stop date \geq study med start date, assign as concomitant
 
Cannot be assigned as 'post treatment'

	Partial	
Impute stop date as latest possible date (i.e. last day of month if day unknown or 31st December if day and month are unknown), then:
 
If stop date < study med start date, assign as prior
 
If stop date \geq study med start date, assign as concomitant
 
Cannot be assigned as 'post treatment'

	Missing	Assign as concomitant
